### Four-week Follow-up

Study participants will return to the laboratory for a brief follow-up session four weeks after Session V5. This session will include an expired air CO reading, collection of saliva and urine samples, and completion of several questionnaires on REDCap.

### Remote Study Participation

Potential subjects who live in North Carolina but do not live close enough to travel to our Center will be able to participate in the study remotely. Interested individuals will complete the online REDCap initial screening survey and provide contact information. The responses of potential participants who agree to be in the study will be reviewed by study staff who will then contact eligible respondents by phone to answer any questions and explain how to electronically sign and date the e-consent form. A PDF copy of the signed consent form will be emailed to participants. Participants will then report to a LabCorp facility close to them to provide a urine sample to test for illegal drugs and pregnancy (for females of child bearing potential). If the urine tests are negative, participants will be sent a CO monitor for measuring carbon monoxide (CO), and study e-cigarette and nicotine patches. Participants will complete surveys (asking about potential side effects, mood, and experiences with the e-cigarettes, patches and their usual brand cigarettes) at five time points, once every 2 weeks, and at follow-up 4 weeks after stopping the use of study e-cigarettes and patches. CO readings will be obtained at screening and evisit 5.

Electronic Screening Survey: Interested individuals will respond to various advertisement strategies (television, social media advertisement, etc.) by completing a public online REDCap screening survey. After reading a brief description of the study in the survey, interested potential participants will complete questions regarding smoking and medical history in order to assess safety and eligibility for participation in the study. Potential participants will be deemed ineligible if they decline to complete the initial online screening survey, fail to leave their contact information, or do not meet eligibility criteria based on survey responses. Eligible individuals interested in participating will be contacted via phone by study personnel to discuss the process of remote e-consent.

eConsent: Because of the nature of this study and the number of questionnaires that participants are expected to complete, we will not recruit potential participants who do not read, are blind or who do not read/understand English. We are not equipped to validate alternate versions of our questionnaires, most of which are not published. Questionnaires cannot be administered orally by a translator or by Technicians to illiterate or blind individuals because the data obtained would not be comparable to self-administered questionnaires.

Over the phone, potential participants who passed the initial screening survey will be given instructions on how to view the electronic REDCap Informed Consent Form (ICF). If eligibility could not be determined based on survey responses, study staff will follow-up concerning any additional information needed to determine eligibility, such as information about medical conditions. Potential participants who are eligible will then be sent a link to the eConsent form via email and will be given an adequate amount of time to thoroughly read the consent form and have any questions answered by study staff. The final section of the consent form will ask participants to make a selection between three choices: 1) I have read the consent document and I wish to participate in the study, 2) I have read the consent document and have questions that I would like answered before I decide whether to participate in the study, or 3) I have read the consent document and I DO NOT wish to participate in the study. If participants have questions about the information contained in the consent form, they will be prompted to contact study staff and NOT sign the consent form. If participants have no questions and select "I have read the consent document and I wish to participant in the study," an additional form will open and participants will provide First Name, Last Name, an electronic signature (with their finger on a touchscreen device or a stylus/mouse on a computer), the date of the signature, and an email address. Participants will also be provided a PDF copy of the electronically signed consent form for their records.

Identity Confirmation: Participants will be contacted via Zoom in order to verify their identity and age by viewing their picture ID. The Zoom session will not be recorded. Identity and age of the participant will be cross-verified with the contact information provided at LabCorp for the initial drug screen/pregnancy test as recorded on results sent by LabCorp to the Duke Center for Smoking Cessation (CSC).

LabCorp Drug/Pregnancy Test: Potential participants who pass the initial screening survey will be asked to go to a local LabCorp facility (information on locations provided to them by research staff) to provide a urine sample for testing of illicit drug use (all participants) and for pregnancy (women of child bearing potential only). Participants will complete this test at no cost to them. Participants will be asked to provide a copy of their driver's licenses/photo ID upon check-in. Results of the test(s) will be sent directly to the study medical providers via the LabCorp Beacon online system. Drug screens and pregnancy tests must be negative in order for participants to continue in the study.

CO Monitor: Participants who are still eligible after drug and pregnancy screens will be sent a carbon monoxide (CO) monitor (Covita micro basic Smokerlyzer, valued at \$620). Study staff will also provide troubleshooting recommendations for possible problems that may arise. Participants will be asked to use the CO monitor to obtain a CO reading during a Zoom meeting with research staff. The research staff will write the CO reading displayed on the monitor on a study visit form. The Zoom meeting will not be recorded. The initial CO measurement, evaluated by study staff, will be used to determine whether participants meet the minimum CO inclusion requirement. Participants will also complete preliminary questionnaires on REDCap, including smoking history and demographic information.

Randomization and E-cigarette Distribution: After the 1-week training/baseline period is complete and any concerns or questions about the CO monitoring have been addressed, the participants will be assigned a participant number that will determine their randomly assigned study condition, and will be sent by study staff the first shipment of study patches and e-cigarette devices and cartridges containing e-liquid corresponding to their group assignment (nicotine containing e-cigarettes vs. zero-nicotine e-cigarettes). Packages containing nicotine patches and e-cigarettes and liquids require signature by someone who is 21 years of age or older for delivery; the packages will not be delivered if no one appropriate is available to sign for them. This supply will be designed to last through the first 4 weeks of the study; if participants remain in the study, they will be sent a second shipment to use for the final 4 weeks.

Study Milestones: Remote participants will complete study milestones ("e-visits") that correspond to the study visits attended by local participants: baseline, week 2, week 4, week 6 and week 8, plus 4-week follow-up; they will take approximately one hour each to complete and include the same questionnaires that are completed at the in-person study visits, as well as a CO measurement at e-visit 5. The first (baseline) study milestone (V1) will take place after the participants receive their first shipment of e-cigarettes but before they start using them. At this time, participants will be called by study staff and given instructions on how to use the e-cigarettes. They will be asked to switch from cigarette use to use of e-cigarettes during the study. They will then be instructed on the use of daily self-report diaries to be completed on paper. In these diary entries, participants will record the number of conventional cigarettes smoked each day and the number of occasions of e-cigarette use (an occasion defined as taking at least one puff). Participants will be emailed a survey link to complete the questionnaires online via REDCap. Participants will have 72 hours to complete the survey until it expires and it is considered a "missed milestone"; if participants miss two consecutive milestones they will be withdrawn from the study. The

diary entries will be reported to the research staff by phone after e-visit online surveys have been completed.

Each subsequent study milestone (V2-V5) will occur 2 weeks after the previous one, with the follow-up milestone occurring 4 weeks after milestone 5. Participants will be sent a link by email on each study milestone date with instructions to complete the REDCap questionnaires. After the second milestone is completed, participants will be sent a second shipment of e-cigarette cartridges to use until the end of study. At the time of the baseline and final milestones (V1 and V5) and follow-up, participants will be asked to collect a urine sample for NNAL analysis and a saliva sample for analysis of smoking related chemicals (e.g., cotinine), and send these samples to the Duke CSC via UPS.

Participants will be called within 3 days after the first day of study intervention to make sure the study products are being used as directed as well as to ask about any study related side effects. Any reports of side effects, in addition to responses to the Side Effects Form completed online at the study milestones, will be reviewed by the study medical provider. The provider will call the participant if any of the side effects require follow up.

Return and Re-use of the CO monitor: Participants will be asked to return the CO monitor after the CO reading has been obtained during the screening process. If they are accepted into the study and complete e-visits 1-4, then a CO monitor will be sent to them to obtain the CO reading at e-visit 5. The participant will be asked to return the CO monitor after e-visit 5. Upon return of the CO monitor, research staff will disinfect the monitor before sending it to another participant.

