### Sessions

The first study visit (V1) will take place approximately one week after the screening visit. Subjects will complete baseline questionnaires and will be randomized to one of the two groups. Subjects will be tested for exhaled air carbon monoxide, and saliva samples will be collected for analysis of smoking related chemicals (e.g., cotinine). Subjects will also complete questionnaires assessing their dependence on cigarettes (Fagerström Test for Nicotine Dependence (FTND) (Heatherton et al., 1991)), and rewarding effects of cigarettes (modified Cigarette Evaluation Questionnaire (Cappelleri et al., 2007)).

Subsequent study visits will occur approximately two weeks apart (with a five-day window on either side of the scheduled visit). If a participant does not attend a visit and it cannot be rescheduled within the allowable window, the visit will be considered a missed visit; if participants miss two consecutive visits they will be withdrawn from the study. Participants will be tested for exhaled air carbon monoxide, and will also complete questionnaires assessing their dependence on cigarettes (Fagerström Test for Nicotine Dependence (FTND) (Heatherton et al., 1991)), and rewarding effects of cigarettes (modified Cigarette Evaluation Questionnaire (Cappelleri et al., 2007)).

Questionnaires will be completed within REDCap on a desktop computer in the Center office. The technician will log on to the REDCap site and will open the questionnaires for the subjects. Subjects will only have access to their questionnaires. Access to any other websites will be blocked by Duke Psychiatry Information Technology.

At the first (V1) and final (V5) sessions, participants will provide saliva and urine samples. The saliva sample will be used for analysis of smoking related chemicals (e.g., cotinine). The urine sample will be used to assess total urinary 4-(methylnitrosamino)-1-(3-pyridyl)-1-butanol (NNAL), a metabolite of the tobacco-specific carcinogen 4-(methylnitrosamino)-1-(3-pyridyl)-1-butanone (NNK). The half-life of NNAL is 10 days (Goniewicz et al., 2009), yielding a valuable index of sustained reductions in cigarette smoking. The half-life of expired air CO, in contrast, is 4.5 h (Sandberg et al., 2011). Total urinary nicotine equivalents (a measure of total nicotine intake) will also be assessed.

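### Remote V1 questionnaires, urine and saliva are collected after allocation and can be missed or altered by early product use; read literally, a missed e-visit 1 also forfeits the final CO reading

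*Combined protocol and SAP*

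**What the plan says.** **In person** (Sessions). At V1, "Subjects will complete baseline questionnaires and will be randomized to one of the two groups". CO and saliva at V1 are described after that sentence, and V1 urine further on, with no stated order relative to randomisation. Product is dispensed from V1.

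**Remote** (Remote Study Participation). The order is:

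- Screening: CO read over Zoom, plus smoking history and demographics.
- "After the 1-week training/baseline period is complete" and any concerns about CO monitoring are settled, "the participants will be assigned a participant number that will determine their randomly assigned study condition". The first shipment, matched to the arm, then goes out.
- The milestone labelled baseline (V1) "will take place after the participants receive their first shipment of e-cigarettes but before they start using them".
- At V1, staff call to explain the e-cigarettes. "They will be asked to switch from cigarette use to use of e-cigarettes during the study". A survey link is emailed, and "Participants will have 72 hours to complete the survey until it expires", after which the milestone counts as missed.
- For V1, V5 and follow-up, "participants will be asked to collect a urine sample for NNAL analysis" and a saliva sample, and to ship both. No deadline for the samples is given.
- A single missed milestone does not end participation: "if participants miss two consecutive milestones they will be withdrawn from the study".
- The paragraph on return and re-use of the CO monitor provides a monitor for e-visit 5 to accepted participants who have completed all four preceding e-visits.

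**Analysis** (Data Analysis & Statistical Considerations). Expired CO is the main index of combustible use, which is a primary outcome. NNAL is a secondary measure assessed at V1 and V5. Covariates include baseline combustible use, demographics and smoking history. The section gives no rule for a missing baseline value.

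**The concern.** A baseline measure should be fixed before allocation, so that neither its value nor its presence can depend on the arm. In person, V1 cannot be missed after randomisation, because randomisation happens at that visit. For remote participants both safeguards are absent for everything first collected at V1.

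Three things are at stake:

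- **Missing baseline.** A participant can be randomised and stay in the study with no baseline FTND, cigarette evaluation, NNAL or cotinine.
- **Altered baseline.** The request to switch comes in the V1 call, while the survey may still be open and the samples not yet taken. The participant then holds patches and pods. NNAL and cotinine would both respond to early use.
- **Loss of a primary outcome.** If the condition for sending the e-visit 5 monitor is applied as written, missing e-visit 1 alone removes the final CO reading from someone who is still enrolled.

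**Working it through.** **1. Which remote baselines follow allocation**

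| Item | When collected remotely | Relative to randomisation |
|---|---|---|
| Expired CO | Screening | Before |
| Smoking history, demographics | Screening | Before |
| FTND, modified Cigarette Evaluation Questionnaire | V1 | After |
| Urine NNAL, saliva cotinine | V1 | After |

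The exposure is therefore confined to the last two rows. What is recorded in the one-week training and baseline period, beyond CO monitoring and the screening forms, is not stated.

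**2. Can V1 be missed without withdrawal?** Yes. The survey closes after 72 hours, and withdrawal needs two consecutive misses. Someone who misses V1 and completes V2 stays in. The extra $15 for e-visit 1 (Subject Compensation) rewards completion but does not hold back product.

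**3. Does missing V1 reach the primary outcome?** Remote CO is read only at screening and e-visit 5. If all of e-visits 1 to 4 must be complete before a monitor is sent, missing V1 leaves no monitor and so no final CO.

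**4. How far could early use move NNAL?** The plan gives a half-life of 10 days. The fall after t days without smoking is 1 − 2^(−t/10). Take t = 3, borrowing the 72-hour survey window because the samples have no window of their own: 1 − 2^(−0.3) = 18.8%. This assumes that the person stops smoking completely at the start of the window and gives the sample at its end.

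**5. What would lost CO readings cost? (illustration only)**

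The plan's own figure first: 50 per group, effect size 0.5 (taken as a difference in SD units), one-sided alpha 0.05. Power = Φ(0.5 × √(50/2) − 1.645) = Φ(0.855) = 0.804, which agrees with the stated 80%. A noncentral t calculation gives 0.799. With all 65 per group, the normal formula gives 0.886.

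The documents give neither the remote share nor the missed-V1 rate. Assume that 25% to 75% of participants are remote, that 5% to 20% of those miss V1, that losses are equal by arm, and that each miss costs the final CO. The fraction kept is 1 − share × rate:

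- Smallest loss: 1 − 0.25 × 0.05 = 0.9875. From 65 per group, 64.2 remain (power 0.883); from 50, 49.4 remain (0.799).
- Largest loss: 1 − 0.75 × 0.20 = 0.85. From 65 per group, 55.2 remain (power 0.837); from 50, 42.5 remain (0.745).

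The rows from 50 apply if 50 per group is already the number left after other dropout.

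**The case against.** The strongest reply is that the covariates named in the plan are not shown to come from remote V1. CO, smoking history and demographics are all taken at screening, before the arm is fixed. None of the V1 measures is named as a covariate; FTND might count as smoking history, but the plan does not say so. This stands. A reader might infer that the primary model is adjusted for a contaminated baseline, or that a missed V1 removes people from that model for want of a covariate. The documents do not support either inference.

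Second, V1 is meant to precede first use, and participants are blinded (Emergency Unblinding). Both arms receive active patches and the same request to switch. Contamination therefore requires a departure from the planned order, and it biases the comparison only if early use changes smoking differently by arm within days. This also stands. A reader might infer that the treatment effect is necessarily pulled towards zero. That would follow only if early use cut smoking more in the nicotine arm and the analysis adjusted for, or took change from, V1. If early use acted equally in both arms, it would mainly add noise. The plan specifies no change-from-V1 analysis of NNAL.

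Third, a larger NNAL distortion could be computed for a longer delay (29% at five days, by the same formula), but no document gives a five-day delay.

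Fourth, the contrast with in-person participants is firm only for questionnaires. The in-person order of saliva and urine relative to randomisation is not stated.

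None of this answers the sequence itself, the possibility of missing V1 after allocation, or the condition attached to the e-visit 5 monitor.

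**Conclusion.** The point holds in a limited form. For remote participants, the V1 questionnaires, NNAL and cotinine are collected after randomisation and after product has arrived. They can be missed without withdrawal, or altered by early use that no described check would detect. Read literally, a missed e-visit 1 also costs the primary CO reading at e-visit 5; a looser reading, in which the monitor goes to anyone still enrolled, would remove that consequence, so the wording needs settling.

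Remote baseline CO, smoking history and demographics are not affected. The NNAL distortion of up to 19% is one person's worst case under complete cessation for three days, not an estimate of bias. Bias between arms is possible but cannot be sized, because the remote share, the missed-V1 rate and the rate of early use are not given. The power figures above depend on assumed rates and on the literal reading of the monitor rule.

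**What to change.** - Collect the remote V1 questionnaires, urine and saliva within the existing one-week training and baseline period. Assign the participant number and release the first shipment only once they are complete.
- Keep the product-instruction call after delivery.
- Send the e-visit 5 CO monitor to every randomised remote participant still in the study, whether or not each earlier e-visit was completed.

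The plan already ties shipments to milestones: the second supply follows the second e-visit. Holding the first shipment in the same way is a reordering, not a new procedure.

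Costs: a possible delay of a few days before shipment, and loss of non-responders before randomisation rather than after it. There is also a mailing cost. If sample kits travel with the screening CO monitor, some go to people who then fail the CO criterion; otherwise one extra mailing is needed once CO eligibility is confirmed. Sending more monitors for e-visit 5 adds some shipping.

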The primary outcome measures will be the amount of combustible cigarette use and e-cigarette use in the last week of the 8-week exposure period. The main index of combustible cigarette use will be expired air CO. Self-reported cigarettes/day recorded on diaries will be a secondary index of cigarette consumption. The main index of e-cigarette use will be the number of cartridges consumed, based on self-report and counts of the number of unused e-cigarette tanks returned.

Continuing to smoke carries significant health risks. Subjects enrolling in this study are not being asked to quit smoking over the course of the study, but will be exposed to no additional risk from their usual smoking behavior. Their exposure to harmfully and potentially harmful constituents in combustible cigarettes may decrease to the extent they use e-cigarettes as an alternative to combustible cigarettes.

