Although subjects receiving nicotine from e-cigarettes will no doubt receive a range of nicotine doses, depending on the extent of use, data from previous studies (Shahab et al., 2017) suggests that the mean dose is expected on average to be similar to that provided by a 21 mg/day patch (and actual mg/day, as estimated from the number of e-liquid cartridges consumed, will be a covariate in the statistical analyses.).

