### Design Overview

The study will comprise a randomized, double-blind parallel-arm study to ascertain the role of nicotine dose and route of administration in reducing use of combustible cigarettes and in facilitating adoption of e-cigarettes. One hundred thirty daily cigarette smokers will be randomly assigned to receive 8 weeks of exposure to the following conditions (65/group):

- 1. Nicotine containing e-cigarettes + 21 mg nicotine skin patches
- 2. Zero-nicotine e-cigarettes + 21 mg nicotine skin patches

Nicotine and non-nicotine e-cigarettes will be purchased from JUUL Labs. The JUUL is a rectangular closedsystem e-cigarette. This e-cigarette was commercially available as of August 8, 2016 and does not contain any alterations to the chemistry or physical characteristics. Each JUUL Pod pack contains 4 pods. Each JUUL Pod contains 0.7mL with 5% nicotine by weight, approximately equivalent to one pack of cigarettes or 200 puffs. Multiple flavors will be used in this study in order to more accurately mimic real world conditions. Subjects will receive packs containing tobacco-flavored and mint-flavored or menthol-flavored pods. Subjects will be provided with enough additional packs of pods to use during the smoking period. JUUL Pods are sealed system cartridges for use in the JUUL e-cigarette. Each pod is contained in tamper resistant blister packs. The nicotine patches will be purchased from Duke Outpatient Pharmacy.

Ad libitum smoking will be assessed weekly using daily diary recordings of cigarettes smoked per day as well as the objective index of expired air carbon monoxide (CO) levels measured at the study visits.

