### **Data Analysis & Statistical Considerations**

 Describe endpoints and power calculations. Provide a detailed description of how study data will be analyzed, including statistical methods used, and how ineligible subjects will be handled and which subjects will be included for analysis. Include planned sample size justification. Provide estimated time to target accrual and accrual rate. Describe interim analysis including plans to stop accrual during monitoring. Phase I studies, include dose escalation schema and criteria for dose escalation with definition of MTD and DLT.

The primary outcome measures will be the amount of combustible cigarette use and e-cigarette use in the last week of the 8-week exposure period. The main index of combustible cigarette use will be expired air CO, a highly sensitive and specific measure of smoke inhalation. As a secondary measure (at the first (V1) and final (V5) sessions), we will assess total urinary 4-(methylnitrosamino)-1-(3-pyridyl)-1-butanol (NNAL), a metabolite of the tobacco-specific carcinogen 4-(methylnitrosamino)-1-(3-pyridyl)-1-butanone (NNK). The half-life of NNAL is 10 days (Goniewicz et al., 2009), yielding a valuable index of sustained reductions in cigarette smoking. The half-life of expired air CO, in contrast, is 4.5 h (Sandberg et al., 2011).

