Self-reported cigarettes/day recorded on diaries will also be a secondary index of cigarette consumption. The main index of e-cigarette use will be the number of cartridges consumed, based on selfreport and counts of the number of unused e-cigarette tanks returned. We hypothesize that e-cigarette use will be higher, and concomitantly, combustible cigarette use will be lower, in the nicotine e-cigarette condition compared to the zero-nicotine e-cigarette condition (i.e., comparing Group 1 vs. Group 2). This hypotheses will be evaluated using General Linear Modeling (GLM) techniques to assess the significance of the nicotine factor, using a 1-tailed alpha=0.05. A one-tailed comparison is justified given that a higher dose of nicotine in the e-cigarette would only be expected to decrease use of conventional cigarettes. Moreover, there would be no interest in pursuing the nicotine e-cigarette plus nicotine patch combination if it led to greater smoking than the placebo e-cigarette plus nicotine patch. Thus, the 5% Type I error rate can reasonably be assigned to the 1-tailed comparison. Covariates in the analysis of combustible cigarette use will include the amount of e-cigarette use, since that will affect the overall dose of nicotine received by subjects, as well as baseline combustible cigarette use, and baseline demographic and smoking history variables (the latter will also serve as covariates in the analysis of e-cigarette use as a dependent measure). We predict at least a moderate effect size (0.5) for each of the main effects, nicotine and route of administration, so that a sample size of 50 per group will yield at least 80% power to detect the hypothesized effects.

• Summarize safety concerns, and describe the methods to monitor research subjects and their data to ensure their safety, including who will monitor the data, and the frequency of such monitoring. If a data monitoring committee will be used, describe its operation, including stopping rules and frequency of review, and if it is independent of the sponsor (per 45 CFR 46.111(a) (6)).

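### The remote diary records occasions of e-cigarette use, while the primary e-cigarette index is cartridges consumed and no remote cartridge count is described

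*Combined protocol and SAP*

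**What the plan says.** The Data Analysis & Statistical Considerations section sets the primary outcomes as "the amount of combustible cigarette use and e-cigarette use in the last week of the 8-week exposure period". It then states: "The main index of e-cigarette use will be the number of cartridges consumed". The sources, given there and in the Research Abstract, are "based on self-report and counts of the number of unused e-cigarette tanks returned". Neither place makes an exception for remote participants.

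The two participation modes collect different things:

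- **In person (Sessions; Subject Compensation).** The take-home diary covers cigarettes per day and cartridges used. Used and unused pods are to be brought to the next visit, and a per-visit payment is tied to returning diary and product.
- **Remote (Remote Study Participation).** For the paper diary, "participants will record the number of conventional cigarettes smoked each day and the number of occasions of e-cigarette use". An occasion is one puff or more. Entries are read to staff by phone after each e-visit survey. The items to be sent back are the CO monitor and the urine and saliva samples. The e-visits use the same questionnaires as the in-person visits, but no cartridge item is named.

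E-cigarette use also enters the CO analysis: "Covariates in the analysis of combustible cigarette use will include the amount of e-cigarette use". That sentence gives no unit. The Background & Significance section describes the covariate as mg/day, which, "as estimated from the number of e-liquid cartridges consumed, will be a covariate in the statistical analyses".

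**The concern.** A primary outcome needs a value in one unit for every randomised participant. As written, the remote procedures produce occasions and the primary index is in cartridges. No conversion is given, and no separate analysis of remote participants is planned.

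Two things are at stake. First, remote participants may have no value on the primary e-cigarette index, or may have occasions pooled with cartridges as though they were comparable. Second, the gap can reach the other primary outcome. Remote participants have CO measured at e-visit 5, but the CO model carries e-cigarette use as a covariate. If that covariate is cartridge-based and incomplete rows are dropped, a participant with a valid CO reading could leave the CO analysis because a cartridge figure is missing. The documents state neither that rule nor any other method for missing data.

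**Working it through.** **1. Sources of the index, by mode**

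| Source of the primary index | In person | Remote |
|---|---|---|
| Self-reported cartridges | Diary | Not described; diary records occasions |
| Count of unused pods | Pods returned at visits | Not described |
| Payment tied to product return | Yes | None itemised |

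The itemised remote payments already add up to the stated total: 35 + (5 × 25) + 15 + 5 + 30 + (5 × 5) + (2 × 50) = $335. No product-return item is left over. This is consistent with no return being requested, but does not prove it.

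**2. Can occasions be converted to cartridges?**

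Design Overview describes a pod as "approximately equivalent to one pack of cigarettes or 200 puffs". A conversion would therefore be

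pods = occasions × (puffs per occasion) / 200.

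The middle term is not recorded. By definition it is at least 1, and no upper limit is given, so the same diary entry fits very different numbers of pods. No assumed value is needed to see this.

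**3. Can shipments stand in for consumption?**

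Supplies go out in two shipments, each meant to last four weeks. The amount sent caps consumption. Without a count of what remains, it gives neither total use nor last-week use.

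**4. Precision, as an illustration**

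Inputs from the documents: 65 randomised per group, effect size 0.5, one-tailed alpha 0.05, and the statement that "a sample size of 50 per group will yield at least 80% power to detect the hypothesized effects". The remote share f is not stated. The illustration assumes the same f in both arms, no usable e-cigarette value from remote participants, and no other loss.

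The normal approximation is power = Φ(0.5 × √(n/2) − 1.645).

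- Plan's own figure, n = 50: Φ(2.500 − 1.645) = 0.804. It reproduces; the t-test version gives 0.799.
- All randomised, n = 65: Φ(2.850 − 1.645) = 0.886.

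The margin above 50 is used up at f = (65 − 50)/65 = 15/65 = 23.1%. With n = 65 × (1 − f):

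| Assumed remote share | n per group | Power |
|---|---|---|
| 10% | 58.5 | 0.855 |
| 20% | 52 | 0.817 |
| 30% | 45.5 | 0.770 |
| 40% | 39 | 0.713 |

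The documents do not say what the gap between 50 and 65 is meant to cover. Any ordinary dropout would lower the 23% threshold.

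**The case against.** The best defence is that the data may be collected somewhere the protocol does not spell out. Remote e-visits use the in-person questionnaires, and those forms are not in the file. The Research Abstract says in-person visits collect the use outcomes and then gives online questionnaires as the remote alternative, which can be read as the questionnaires taking over that task. Self-report is one of the two named sources, so a remote participant does not need to return pods to have a value. This stands as a limit on certainty: the documents show a conflict in the description, not that the data are absent. It does not remove the conflict. In person, the diary is the instrument described as holding cartridges, and the remote diary is the one given another unit. The remote surveys are described as covering side effects, mood and product experiences, with no count of cartridges.

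It can also be said that occasions are recorded in both randomised arms, so the arms could be compared within the remote group. That is true, but no such analysis is planned, and it would not be on the primary index.

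A reader might infer a bias between arms. The documents do not support that. Remote participation depends on where a person lives, which is settled before randomisation, and the same diary is used in both arms.

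A reader might also infer a one-sided loss from the CO model, because on the mg/day reading zero-nicotine pods give 0 mg whatever the count, leaving only nicotine-arm values unknown. That needs two things the documents do not settle: that mg/day is the unit used, and that incomplete rows are dropped. Nor can its cost be read from an unadjusted two-sample power calculation, because a covariate that is zero throughout one arm is strongly tied to arm.

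**Conclusion.** The concern holds as a conflict between the remote diary's unit and the primary e-cigarette index, and should be fixed. Confidence is moderate, because the consequence depends on whether the questionnaires contain an unnamed cartridge item. If they do not, remote participants have no value on that index or on a cartridge-based covariate.

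The demonstrated problem is comparability. The loss of precision cannot be sized from the documents; the 23% threshold is an illustration under the assumptions listed with it. The effect on the CO analysis is conditional on a cartridge-based covariate and on dropping incomplete rows. The text does not support going further and saying that remote data are already lost or that the treatment comparison is biased.

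**What to change.** 1. Add cartridges used to the remote diary, in the same unit and wording as the in-person diary, and keep occasions alongside. Collect it in the phone call already planned after each e-visit. If an existing questionnaire holds a cartridge item, name it in the Remote Study Participation and Data Analysis sections instead.
2. In the Data Analysis section, make self-reported cartridges the common measure for both modes, and keep the pod counts where pods are returned. State how participants without cartridge data are analysed, so that a missing cartridge value does not remove anyone with a measured CO from the CO comparison.

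The cost is one diary line, slightly more burden for remote participants, and a short addition to the analysis text that also settles the common measure for in-person participants. Remote participants who have already finished cannot be recovered from occasions unless an existing form holds cartridges. They should be reported as having no cartridge value.
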